11.1 Regulatory and Ethical Conduct of the Study

The study will be performed in accordance with the ethical principles that have their origin in the Declaration of Helsinki, International Council for Harmonisation (ICH) Good Clinical Practice (GCP), and all applicable regulations.

11.2 Independent Ethics Committee or Institutional Review Board

Federal regulations and ICH guidelines require that approval be obtained from an institutional review board (IRB)/IEC before participation of human patients in research studies. Before study onset, the protocol, informed consent, advertisements to be used for the recruitment of study patients, and any other written information regarding this study intended to be provided to the patient or the patient's legally authorized representative must be approved by the IRB/IEC. Documentation of all IRB/IEC approvals will be maintained by the site and will be available for review by the Sponsor or its designee.

All IRB/IEC approvals should be signed by the IRB/IEC chairman or designee and must identify the IRB/IEC name and address, the clinical protocol by title or protocol number or both, and the date approval or a favorable opinion was granted.

The Investigator is responsible for obtaining continued review of the clinical research as specified by the IRB/IEC, at intervals not exceeding 1 year. The Investigator must supply the Sponsor or its designee with written documentation of continued review of the clinical research.

11.3 Patient Information and Consent

Informed consent in compliance with IRB/IEC and local regulations shall be obtained from each patient or their legally authorized representative before performing any study procedures and will be documented with a signed IRB/IEC approved ICF. Before enrollment, each prospective patient or his or her legally authorized representative will be given a full explanation of the study and be allowed to read the approved ICF. Once the Investigator is assured that the patient/legally authorized representative understands the implications of participating in the study, the patient/legally authorized representative will be asked to give consent to participate in the study and sign the ICF. The process for obtaining consent has to be documented at the institution.

If the ICF is revised during the course of the study, all patients on-study, including those in follow-up, must sign the revised form, unless otherwise indicated by the IRB/IEC (local or global, as applicable). In such case, the reason for not re-consenting the patient should be documented.

11.4 Confidentiality

All laboratory specimens, evaluation forms, reports, and other records will be identified in a manner designed to maintain patient confidentiality. All records will be kept in a secure storage area with limited access. Clinical information will not be released without the written permission of the patient (or the patient's legal guardian), except as necessary for monitoring and auditing by the Sponsor, its designee, regulatory authorities, or the IRB/IEC.

The Investigator and other study staff may not disclose or use for any purpose other than performance of the study any data, record, or other unpublished, confidential information disclosed to those individuals for the purpose of the study. Prior written agreement from the Sponsor or its designee must be obtained for the disclosure of any said confidential information to other parties.

11.5 Financial Disclosure and Obligations

Investigators are required to provide financial disclosure information to allow the Sponsor to submit the complete and accurate certification or disclosure statements as required under 21 CFR 54 and local regulations. In addition, the Investigator must promptly update this information if any relevant changes occur during the course of the investigation and for 1 year following the completion of the study.

11.6 Serious Adverse Events Report Requirements

The Sponsor will ensure that all relevant safety information (SAEs and SUSARs) is reported to the FDA and competent authorities of European Member States, and to the IRB/IEC, in accordance with current legislation.

11.7 Study Conduct

The Investigator will conduct all aspects of this study in accordance with the principles of the current version of ICH E6 as well as all national, state, and local laws and regulations. Study personnel involved in conducting this study will be qualified by education training and experience to perform their respective tasks. Study information from this protocol will be posted on publicly available clinical study registers before enrollment of patients begins.

11.8 Protocol Amendments

Any change in the study plan requires a protocol amendment. All amendments to the protocol must be reviewed and approved following the same process as the original protocol before the amended protocol can be implemented. The Investigator will inform the governing IRB/IEC of all protocol amendments issued by the Sponsor in accordance with established IRB/IEC procedure. Only protocol amendments intended to eliminate an apparent immediate hazard to patient(s) may be implemented immediately, i.e., without IRB/IEC approval, but the circumstances of the change must be documented and submitted to the IRB/IEC.

11.9 Monitoring of the Study

All aspects of the study will be carefully monitored by the Sponsor or designee for compliance with GCP and applicable government regulations.

Investigators and institutions involved in the study will permit study-related monitoring, audits, IRB/IEC review, and regulatory inspections by providing direct access to all study records. In the event of an audit, the Investigator agrees to allow the Sponsor, representatives of the Sponsor, or a regulatory agency access to all study records.

The Investigator should promptly notify the Sponsor and the CRO of any inspections scheduled by any regulatory authorities and promptly forward copies of any inspection reports received to the Sponsor.

11.10 Records Retention

Essential documents should be retained for at least 15 years from the completion of the study (last patient last visit) and until at least 2 years after the last approval of a marketing application in an ICH region and until there are no pending or contemplated marketing applications in an ICH region or at least 2 years have elapsed since the formal discontinuation of clinical development of the investigational study drug. However, these documents should be retained for a longer period if required by the applicable regulatory requirements or by an agreement with the Sponsor. It is the responsibility of the Sponsor to inform the Investigator/institution as to when these documents no longer need to be retained.

13.1 Appendix 1. Eastern Cooperative Oncology Group Performance Status

Performance status will be assessed using the ECOG performance status grades as indicated below:

Grade	Definition
0	Fully active, able to carry on all pre-disease performance without restriction
1	Restricted in physically strenuous activity but ambulatory and able to carry out work of a light or sedentary nature, e.g., light house work, office work
2	Ambulatory and capable of all self-care but unable to carry out any work activities; up and about more than 50% of waking hours
3	Capable of only limited self-care; confined to bed or chair more than 50% of waking hours
4	Completely disabled; cannot carry on any self-care; totally confined to bed or chair
5	Dead

[Oken et al., 1982](#)

13.2 Appendix 2. Response Assessment of Hodgkin and Non-Hodgkin Lymphoma (Lugano Classification)

Response / Site	PET-CT-Based Response	CT-Based Response
Complete	Complete metabolic response	Complete radiologic response (all of the following)
Lymph nodes and extralymphatic sites	
 Score 1, 2, or 3* with or without a residual mass on 5PS** 
Note: Uptake may be greater than normal mediastinum and/or liver in Waldeyer's ring or extranodal sites with high physiologic uptake or with activation within spleen or marrow (e.g., with chemotherapy or myeloid colony-stimulating factors). In this circumstance, complete metabolic response may be inferred if uptake at sites of initial involvement is no greater than surrounding normal tissue even if the tissue has high physiologic uptake
	
 Target nodes/nodal masses must regress to ≤ 1.5 cm in LD No extralymphatic sites of disease
Nonmeasured lesion	
 Not applicable 	
 Absent
Organ enlargement	
 Not applicable 	
 Regress to normal
New lesions	
 None 	
 None
Bone marrow	
 No evidence of FDG-avid disease in marrow 	
 Normal by morphology; if indeterminate, IHC negative
Partial	Partial metabolic response	Partial remission (all of the following)
Lymph nodes and extralymphatic sites	
 Score 4 or 5** with reduced uptake compared with baseline and residual mass(es) of any size. At interim, these findings suggest responding disease. At end of treatment, these findings indicate residual disease. 	
 $\geq 50\%$ decrease in SPD of up to 6 target measurable nodes and extranodal sites When a lesion is too small to measure on CT, assign 5 mm \times 5mm as the default value. When no longer visible, 0 \times 0 mm For a node >5 mm \times 5 mm, but smaller than normal, use actual measurement for calculation
Nonmeasured lesion	
 Not applicable 	
 Absent/normal, regressed, but no increase
Organ enlargement	
 Not applicable 	
 Spleen must have regressed by $>50\%$ in length beyond normal
New lesions	
 None 	
 None
Bone marrow	
 Residual uptake higher than uptake in normal marrow but reduced compared with baseline (diffuse uptake compatible with reactive changes from chemotherapy allowed). If there are persistent focal changes in the marrow in the context of a nodal response, consideration should be given to further evaluation with MRI or biopsy or an interval scan 	
 Not applicable
No response or stable disease	No metabolic response	Stable disease

Response / Site	PET-CT-Based Response	CT-Based Response
Target nodes/nodal masses, extranodal lesions	
 Score 4 or 5 with no significant change in FDG uptake from baseline at interim or end of treatment 	
 <50% decrease from baseline in SPD of up to 6 dominant, measurable nodes and extranodal sites; no criteria for progressive disease are met
Nonmeasured lesions	
 Not applicable 	
 No increase consistent with progression
Organ enlargement	
 Not applicable 	
 No increase consistent with progression
New lesions	
 None 	
 None
Bone marrow	
 No change from baseline 	
 Not applicable
Progressive disease	Progressive metabolic disease	Progressive disease (requires at least 1 of the following)
Individual target nodes/nodal masses	
 Score 4 or 5 with an increase in intensity of uptake from baseline and/or 	
 PPD progression
Extranodal lesions	
 New FDG-avid foci consistent with lymphoma at interim or end of treatment assessment 	
An individual node/lesion must be abnormal with:
 
 LDi > 1.5 cm and Increase by $\geq 50\%$ from PPD nadir and An increase in LDi or SDi from nadir 0.5 cm for lesions ≤ 2 cm 1.0 cm for lesions > 2 cm In the setting of splenomegaly, the splenic length must increase by $> 50\%$ of the extent of its prior increase beyond baseline (e.g., a 15-cm spleen must increase to > 16 cm). If no prior splenomegaly, must increase by at least 2 cm from baseline
Nonmeasured lesions	
 None 	
 New or recurrent splenomegaly New or clear progression of preexisting nonmeasured lesions
New lesions	
 New FDG-avid foci consistent with lymphoma rather than another etiology (e.g., infection, inflammation). If uncertain regarding etiology of new lesions, biopsy or interval scan may be considered 	
 Regrowth of previously resolved lesions A new node > 1.5 cm in any axis A new extranodal site > 1.0 cm in any axis; if < 1.0 cm in any axis, its presence must be unequivocal and must be attributable to lymphoma Assessable disease of any size unequivocally attributable to lymphoma
Bone marrow	
 New or recurrent FDG-avid foci 	
 New or recurrent involvement

Abbreviations: 5PS, 5-point scale; CT, computed tomography; FDG, fluorodeoxyglucose; IHC, immunohistochemistry; LDi, longest transverse diameter of a lesion; MRI, magnetic resonance imaging; PET, positron emission tomography; PPD, cross product of the LDi and perpendicular diameter; SDi, shortest axis perpendicular to the LDi; SPD, sum of the product of the perpendicular diameters for multiple lesions.

* A score of 3 in many patients indicates a good prognosis with standard treatment, especially if at the time of an interim scan. However, in trials involving PET where de-escalation is investigated, it may be preferable to consider a score of 3 as inadequate response (to avoid undertreatment). Measured dominant lesions: Up to six of the largest dominant nodes, nodal masses, and extranodal lesions selected to be clearly measurable in two diameters. Nodes should preferably be from disparate regions of the body and should include, where applicable, mediastinal and retroperitoneal areas. Non-nodal lesions include those in solid organs (e.g., liver, spleen, kidneys, lungs), GI involvement, cutaneous lesions, or those noted on palpation. Nonmeasured lesions: Any disease not selected as measured, dominant disease and truly assessable disease should be considered not measured. These sites include any nodes, nodal masses, and extranodal sites not selected as dominant or measurable or that do not meet the requirements for measurability but are still considered abnormal, as well as truly assessable disease, which is any site of suspected disease that would be difficult to follow quantitatively with

measurement, including pleural effusions, ascites, bone lesions, leptomeningeal disease, abdominal masses, and other lesions that cannot be confirmed and followed by imaging. In Waldeyer's ring or in extranodal sites (e.g., GI tract, liver, bone marrow), FDG uptake may be greater than in the mediastinum with complete metabolic response, but should be no higher than surrounding normal physiologic uptake (e.g., with marrow activation as a result of chemotherapy or myeloid growth factors).

** PET 5PS: 1, no uptake above background; 2, uptake \leq mediastinum; 3, uptake $>$ mediastinum but \leq liver; 4, uptake moderately $>$ liver; 5, uptake markedly higher than liver and/or new lesions; X, new areas of uptake unlikely to be related to lymphoma.

[Cheson et al., 2014](#)

2.1 Primary Objectives

Evaluate the efficacy of single agent loncastuximab tesirine in patients with relapsed or refractory DLBCL.

2.2 Secondary Objectives

- Further evaluate the efficacy of loncastuximab tesirine
- Characterize the safety profile of loncastuximab tesirine
- Characterize the pharmacokinetic (PK) profile of loncastuximab tesirine
- Evaluate the immunogenicity of loncastuximab tesirine
- Evaluate the impact of loncastuximab tesirine treatment on health-related quality of life (HRQoL)

[REDACTED]

■ [REDACTED]

■ [REDACTED]

3 Study Design

This is a Phase 2, multi-center, open-label, single-arm study. The study will enroll approximately 140 patients.

A 2-stage design will be used, with an interim analysis for futility on the first 52 patients. If ≥ 10 patients respond (complete response [CR]+partial response [PR]), the study will proceed to complete full enrollment. Enrollment will continue during the interim analysis; however, further enrollment will be halted if futility is confirmed.

3.1 Sample Size Consideration

The primary hypothesis is that the overall response rate (ORR) based on central review for patients treated with loncastuximab tesirine is significantly greater than 20% (i.e., $H_0: p \leq 0.2$ vs. $H_a: p > 0.2$). This hypothesis will be tested at type I error of 0.05 (2-sided).

Using nQuery exact test for single proportion, a sample size of 140 patients has >99% power to achieve a 1-sided significance level of 0.025 (2-sided significance level of 0.05). This sample size will provide adequate precision for observed ORR in the expected range and a robust population for safety evaluation.

3.2 Randomization

This study is not randomized.

3.3 Modifications to the statistical section of the protocol

NA.

4 Statistical methods

All analyses use SAS[®] version 9.4 or higher. All available data will be used in the analyses, and important data will be included in data listings, sorted by patient, and by visit within patient. Missing data will not be imputed, except via censoring in survival analyses and as otherwise specified.

Unless otherwise noted, categorical data will be presented using counts and percentages, with the number of patients in the analysis population as the denominator for percentages. Percentages will be rounded to one decimal place, except 100% will be displayed without any decimal places and percentages will not be displayed for zero counts. Continuous data, unless otherwise noted, will be summarized using the number of observations (n), mean, standard deviation (std), median, minimum, and maximum. Minima and maxima will be rounded to the precision of the original value, and means, medians, and 95% confidence intervals (CIs) if presented will be rounded to 1 decimal place greater than the precision of the original value. The std will be rounded to 2 decimal places greater than the precision of the original value, up to a maximum of 3 decimal places.

4.1 Analysis Populations

4.1.1 All-Treated Population

All patients who receive at least 1 dose of loncastuximab tesirine. This population will be used in the primary analyses of efficacy and safety.

4.1.2 Per-Protocol Population

All patients in the all-treated population who met the inclusion/exclusion criteria, did not take a prohibited concomitant treatment, nor had other protocol deviation which have major impact on efficacy results.

4.1.3 Stem Cell Transplant (SCT) Population

All patients who have responded to loncastuximab tesirine and undergo stem cell transplant (either autologous or allogeneic) after permanent discontinuation of loncastuximab tesirine treatment without any intervening anticancer therapy.

4.1.4 Patient Reported Outcome (PRO) Population

All patients in the all-treated patients with baseline score (at least one instrument) and at least 1 postbaseline score (in at least one instrument).

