4.9.1 Overall Response Rate

Overall response rate is defined as the proportion of patients who achieve either CR or PR as best overall response (BOR) as determined by central review according to the 2014 Lugano Classification criteria before the start of subsequent anticancer therapy or procedure. For the primary ORR analysis in the all-treated population, patients with a CR or PR will be counted as successes and all other patients (including those with missing response information) will be counted as failures.

The order of overall response category is: CR, PR, SD, NE, PD (including disease recurrence/ relapse). The overall response category will be derived based on response assessment performed on or before the start of subsequent anticancer therapy/procedure. Patients without documented subsequent anticancer therapy and/or with missing start date of anticancer therapy will be considered as not having received subsequent anticancer therapy. A BOR of SD can only be made after the patient is on-study for a minimum of 35 days after the first dose of study drug. Any tumor assessment indicating SD before this time period will be considered as NE for BOR if no assessment after this time period is available.

The overall response rate and the corresponding 95% two-sided exact confidence interval will be presented. Subgroup analysis may be provided for disease subtype, disease stage, double/triple hit (yes/no), bulky disease (yes/no), GCB/ABC, transformed (yes/no), age group, sex, country, response to the first line and/or most recent line of prior systematic therapy (relapse: CR+PR vs. refractory: SD+PD vs. other: NE + missing), and other relevant variables.

Percent change from baseline in the sum of product of the perpendicular diameters (SPD) for target lesions will be presented for available data in the all-treated population. These data will also be displayed as a waterfall plot, with vertical bars representing the sorted values of best percent reduction for each patient.

A sensitivity analysis of ORR determined by the independent reviewer's evaluation will be conducted for the per-protocol population if relevant.

A sensitivity analysis of ORR will be conducted in which best overall response is determined by investigators.

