4.10.1 European Quality of life (EuroQol)-5 Dimensions-5 Levels (EQ-5D-5L)

EQ-5D-5L is designed as an international, standardized, generic instrument for describing and evaluating QoL. The EQ-5D-5L consists of two parts:

- The descriptive system: QoL is classified according to five dimensions: mobility, self care, usual activities, pain/discomfort, and anxiety/depression. Each dimension comprises five levels of perceived problems (e.g., none, slight, moderate, severe, extreme).
- The visual analog scale (VAS): patients are asked to indicate their health state today on a VAS with the endpoints labeled 'the best health you can imagine' (score 100) and 'the worst health you can imagine' (score 0). Patients are asked to mark an "X"

on the VAS to indicate their own health and then to report the score in a text box. If there is a discrepancy between where the patient has placed the X and the number he/she has written in the box, the number in the box is to be entered in the CRF together with a comment indicating the discrepancy.

Individual dimension responses will be summarized at each scheduled assessment with frequency counts and percentage of patients.

Descriptive statistics (mean, standard deviation, median and range) of actual values and changes from baseline will be presented at each scheduled assessment for the EQ-VAS.

A change of 7 points in VAS from the baseline is considered minimally important difference (MID) (Pickard et al., 2007). Patients will be classified as improved/deteriorated based on the established MID, i.e., if at least one of the post-baseline scores improves/deteriorates by the magnitude of the MID compared to baseline score. Proportion of patients with improvement/deterioration will be summarized.

Completion rate of EQ-5D-5L will be calculated as the number of patients who complete at least one question of EQ-5D-5L (e.g., either in descriptive system or VAS) divided by the number of patients treated at a visit. Summary of completion rate at each visit will be presented.

Summary analyses will include data up to the start of subsequent anticancer therapy/procedure.

A data listing for each individual dimension response, and the EQ-VAS will be presented for each patient at each visit.

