14.3.8 ECOG DATA TABLE

14.3.8.1 Summary of ECOG Performance Score by Visits (All-Treated Population)

14.3.9 PRO DATA TABLE

14.3.9.1.1 Summary of EQ-5D-5L VAS Score by Visits (PRO Population)

14.3.9.1.2 Frequency Distribution of the Individual Dimension Response from EQ-5D-5L Descriptive System by Visits (PRO Population)

14.3.9.1.3 Summary of Patients Classified as Improvement/Deterioration Based on Minimally Clinically Important Difference for EQ-5D-5L VAS Score (PRO Population)

14.3.9.1.4 Completion Rate for EQ-5D-5L Descriptive System and VAS Score by Visit (PRO Population)

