14.3.9.2.1 Summary of Subscale and Composite Scores from FACT-Lym by Visits (PRO Population)

14.3.9.2.2 Best Change from Baseline in Subscale and Composite Scores from FACT-Lym (PRO Population)

14.3.9.2.3 Summary of Patients Classified as Improvement/Deterioration Based on Minimally Clinically Important Difference for FACT-Lym Subscale and Composite Scores (PRO Population)

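### The HRQoL improved proportion omits treated patients who never returned a post-baseline form, so it runs higher than among all treated patients with a baseline score

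*SAP*

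**What the plan says.** SAP 4.1.4 defines the PRO Population as all-treated patients "with baseline score (at least one instrument) and at least 1 postbaseline score (in at least one instrument".

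For EQ-VAS, SAP 4.10.1 classes a patient as improved or deteriorated "if at least one of the post-baseline scores improves/deteriorates by the magnitude of the MID compared to baseline score", and then states: "Proportion of patients with improvement/deterioration will be summarized". SAP 4.10.2 plans the same kind of summary for FACT-Lym. Neither section names a denominator, so the general rule in SAP 4 applies: percentages are taken "with the number of patients in the analysis population as the denominator for percentages".

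SAP Appendix 2 settles which population that is:
- Table 14.3.9.1.3: "Summary of Patients Classified as Improvement/Deterioration Based on Minimally Clinically Important Difference for EQ-5D-5L VAS Score (PRO Population"
- Table 14.3.9.2.3: "Summary of Patients Classified as Improvement/Deterioration Based on Minimally Clinically Important Difference for FACT-Lym Subscale and Composite Scores (PRO Population"

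On absent data, SAP 4 says "Missing data will not be imputed, except via censoring in survival analyses and as otherwise specified". The proration rule in SAP 4.10.2 fills missing items within a returned form and supplies nothing for a form that was never returned.

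Protocol Table 1 schedules HRQoL on Day 1 of each cycle and at EOT. The first possible post-baseline form is therefore at C2D1 (about Day 22) or at an earlier EOT visit.

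**The concern.** Entry to the denominator depends on something that happens after the first dose and is tied to the outcome. A patient who completes the baseline form and then dies in Cycle 1, or is too ill to complete a C2D1 or EOT form, contributes to neither proportion. The tables therefore describe patients who survived and were well enough to return a later form, whereas the secondary objective concerns the impact of treatment on HRQoL in the trial's patients.

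The SAP takes the other course for ORR, where "all other patients (including those with missing response information) will be counted as failures". It gives no reason for treating the HRQoL responder proportions differently. With no control arm, nothing shows how much of a reported improvement rate comes from this selection.

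**Working it through.** **The plan's own figures.** The documents state no HRQoL rate, target or expected completion, so there is no figure on this point to reproduce. The ORR power claim does reproduce: with 140 patients, 20% against 40% and one-sided 0.025, rejection at 39 or more responders has exact size 0.0158 and power 0.999. Nothing below touches it.

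**Does another planned output restore these patients?**
- Every HRQoL summary table in Appendix 2 is labelled PRO Population, and no all-treated sensitivity version is listed.
- Completion rates are divided by patients treated at the visit, and their tables carry the same label. Early losses do not show there.
- SAP 4.2 and table 14.1.1 report the size of each analysis population. That discloses how many patients are outside the PRO Population, but it mixes those with no baseline score and those with no later score.

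**Proportion improved.** Let q be the proportion improved in the PRO Population. Let f be the share of treated patients with a baseline score who have no post-baseline score. Counting those patients as not improved gives q(1−f), so the planned figure is larger by the factor 1/(1−f). This assumes that baseline scores exist for both instruments or neither. Both q = 40% and f are assumptions.

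| f | 1/(1−f) | 40% becomes | Difference (points) |
|---|---|---|---|
| 5% | 1.05 | 38.0% | 2.0 |
| 7.5% | 1.08 | 37.0% | 3.0 |
| 10% | 1.11 | 36.0% | 4.0 |
| 12.5% | 1.14 | 35.0% | 5.0 |
| 15% | 1.18 | 34.0% | 6.0 |

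In whole patients: if all 140 have a baseline score and 14 return no later form, 50 improved patients are 50/126 = 39.7% as planned and 50/140 = 35.7% on the wider denominator.

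**Is 5% to 15% a reasonable range?** Two figures in the protocol give a rough scale only.
- Protocol 9.1 quotes a historical median survival of 6.1 months. Under exponential survival, death by Day 21 is 1 − 2^(−21/(6.1 × 30.44)) = 7.5%, or 10 to 11 of 140.
- In Phase 1 (protocol 1.3), 126 of 144 treated patients were evaluable for response, so (144 − 126)/144 = 12.5% were not. The reasons are not given, and this is not questionnaire data.

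**Proportion deteriorated.** Let p be the proportion deteriorated in the PRO Population and g the share of excluded patients who in fact died or worsened. The proportion among all with a baseline score is p(1−f) + gf, which differs from p by f(g − p). With p = 40% and f = 10%:
- g = 100%: 46%, so the planned figure is 6 points too low.
- g = 40%: 40%, no difference.
- g = 0%: 36%, so the planned figure is 4 points too high.

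The direction depends on whether g exceeds p, and the documents give neither.

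**The case against.** **The tempting stronger reading.** A reader might infer that both rows are biased in the treatment's favour, and might put a size on the second by setting 40% deteriorated against 43% to 49% deteriorated or lost (f = 5% to 15%), a relative shortfall of 7% to 18%. The documents do not support that. The comparison sets two different quantities side by side and counts every missing form, including administrative ones, as deterioration. Widening the denominator alone would lower the plain deteriorated row, from 40% to 36% at f = 10%. A reader might also take these tables to be the only patient-level HRQoL result. They are not: SAP 4.10.2 and table 14.3.9.2.2 plan each patient's best FACT-Lym change, though again in the PRO Population.

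**The case for leaving the plan alone.**
- The protocol endpoint is change from baseline, which needs a later score. An observed-case population is a declared choice, and the MID proportions are descriptive with no test attached. This stands, and it is why the point is minor. It does not make the planned percentage a statement about treated patients.
- The exclusion is disclosed in SAP 4.2, and SAP 4.8.1.2 tabulates deaths within 30 days of the last dose. This stands as disclosure, but neither output corrects the proportions.
- The affected group is narrow. EOT forms keep some early discontinuers, and one score on either instrument is enough for entry. A member with no later score on the scale in question already stays in the default denominator. All of this reduces f.
- The range for f is weak. Eligibility requires ECOG 0–2 and adequate organ function and excludes bulky disease, so early deaths may be fewer than the historical median implies. This stands; f is an assumption.
- A shift of 2 to 6 points lies inside the 95% half-width at n = 140, 1.96 × √(0.4 × 0.6/140) = 8.1 points. True, but the shift is systematic and goes one way.
- SAP 4.10 refers missing assessments to scoring manuals that are not among the documents. Their content cannot be checked. As written, SAP 4.1.4 removes patients with no later score before such a rule would apply to these tables.

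**Conclusion.** The concern holds for the proportion improved. Population definition, default denominator and table labels together condition that proportion on a post-dose event, and no planned HRQoL output undoes it. Relative to all treated patients with a baseline score, the figure is inflated by 1/(1−f): 1.05 to 1.18 for an assumed f of 5% to 15%. This rests on counting patients without a later score as not improved and on baseline scores being available for both instruments.

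For deterioration the conclusion is conditional. The planned figure is too low only to the extent that excluded patients died or worsened more often than those included. That is likely for deaths and serious illness but not for forms missed administratively, and the size cannot be computed from the documents.

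The endpoint is secondary and descriptive, and the primary ORR test is unaffected. This is a cheap improvement and does not put the trial's main conclusion in doubt.

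**What to change.** In SAP 4.10.1, SAP 4.10.2 and tables 14.3.9.1.3 and 14.3.9.2.3:

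1. Report the proportion improved among all treated patients with a baseline score on that scale, counting those without a post-baseline score on it as not improved.
2. Show *no post-baseline score* as its own row, split into died, discontinued and other.
3. Report *deteriorated or died before a post-baseline form* beside *deteriorated*, without counting administratively missing forms as deterioration.
4. Keep the PRO Population version alongside.

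Defining the denominator per scale also removes the ambiguity created by the at-least-one-instrument wording in SAP 4.1.4.

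The cost is SAP wording and two table shells, with no new data. The downside is a slightly less favourable improved proportion, in which some administratively missing forms count as not improved; the reason split lets a reader see how many.
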